6 STUDY INTERVENTION

6.1 STUDY INTERVENTION(S) ADMINISTRATION

6.1.1 STUDY INTERVENTION DESCRIPTION

The study intervention is ketamine. Per the package insert, “Ketamine is a nonbarbiturate general anesthetic chemically designated *d,l* 2-(0-chlorophenyl)-2-(methylamino) cyclohexanone hydrochloride. It is formulated as a slightly acid (pH 3.5-5.5) sterile solution for intravenous or intramuscular injection in concentrations containing the equivalent of either 10, 50, or 100 mg ketamine base per milliliter and contains not more than 0.1 mg/mL Phemerol® (benzethonium chloride) added as a preservative. The 10 mg/mL solution has been made isotonic with sodium chloride.”⁴⁶

Ketamine is indicated as the sole anesthetic agent for diagnostic and surgical procedures that do not require skeletal muscle relaxation, for the induction of anesthesia prior to the administration of other general anesthetic agents, and for supplementation of low-potency agents such as nitrous oxide.⁴⁶ It is frequently used off-label for other purposes such as sedation in the intensive care unit and for analgesia.

This trial involves use of an FDA-approved drug for a purpose not listed on the package insert. This trial is exempt from IND requirements because it meets all the criteria in CRF 312.2(b):

- The investigation is not intended to be reported to the FDA to support a new indication or to change the drug labeling.
- The drug is lawfully marketed in the United States as a prescription drug product.
- The investigation does not involve a route of administration, a dosage level, or a patient population that significantly increases the risks compared to the labeled indication.
- The investigation complies with the requirements for IRB review and informed consent.
- The investigation is not intended to promote or commercialize the drug product.

6.1.2 DOSING AND ADMINISTRATION

The study intervention consists of a bolus loading dose followed by a continuous infusion. For patients in the intervention group, the bolus loading dose will consist of ketamine 0.5 mg/kg administered intravenously over 10 minutes (or over 20 minutes if BMI > 40). This will be followed by a continuous infusion at 0.3 mg/kg/h for an additional 2 hours 50 minutes.

Patients in the control group will receive an equal volume of normal saline. The bolus loading dose will consist of normal saline 0.1 mL/kg administered intravenously over 10 minutes (or over 20 minutes if BMI > 40). This will be followed by a continuous infusion at 0.06 mL/kg/h for an additional 2 hours 50 minutes.

Study intervention dosing will be based on actual body weight.

Timing of study medication administration will be the same for both groups. For patients who are extubated in the operating room, the study medication will be initiated prior to leaving the operating room. For patients who remain intubated and transfer to the intensive care unit, the study medication will be administered based on the following criteria:

- If the patient is extubated before 07:00am on postoperative day 1, the study medication will be administered between 05:00am and 08:00am on postoperative day 1.
- If the patient is extubated after 07:00am on postoperative day 1 and before 07:00am on postoperative day 2, the study medication will be administered between 05:00am and 08:00am on postoperative day 2.
- If the patient is extubated after 07:00am on postoperative day 2 and before 07:00am on postoperative day 3, the study medication will be administered between 05:00am and 08:00am on postoperative day 3.
- If the patient remains intubated at 07:00am on postoperative day 3, the patient will be withdrawn from the study.

In the operating room, the study medication will be administered by the anesthesiology clinician (MD or certified registered nurse anesthetist). In the PACU or ICU, the study medication will be administered by the patient's bedside nurse.

Richmond Agitation and Sedation Scale (RASS) scores will be monitored per standard nursing protocols, as described in section 8.2. If the patient experiences sedation to a RASS score ≤ -2 , then the study medication will be halted and the procedures documented in section 7.1 will be followed.

If the RASS score is ≤ -2 before initiation of the study medication, then the study medication will not be initiated at that time. The patient will be re-evaluated the following day, and the study medication will be initiated when the RASS is no longer ≤ -2 . If RASS remains ≤ -2 on postoperative day 3, the patient will be withdrawn from the study.

6.2 PREPARATION/HANDLING/STORAGE/ACCOUNTABILITY

6.2.1 ACQUISITION AND ACCOUNTABILITY

Ketamine will be purchased in multidose vials through the BJH Investigational Drug Service. The study medication (ketamine or normal saline) will be prepared by the Investigational Drug Service after an order has been placed in Epic by the research team. The study medication will be delivered to the

patient's bedside nurse by the Investigational Drug Service utilizing a controlled substance chain of custody form. Any unused study medication will be returned to the Investigational Drug Service and destruction of unused ketamine will be done in accordance with federal, state, and institutional regulations.

6.2.2 FORMULATION, APPEARANCE, PACKAGING, AND LABELING

Ketamine hydrochloride is a 50 mg/mL sterile solution that is clear, colorless, and free of visible particles. It will be purchased in multidose vials containing 500 mg in 10 mL. Ketamine will be manufactured by PAR Pharmaceuticals.

Normal saline is a sterile, preservative free solution that is clear, colorless, and free of visible particles. It will be manufactured by Baxter Healthcare.

6.2.3 PRODUCT STORAGE AND STABILITY

Per the package insert, ketamine is to be stored at a temperature between 20°C and 25°C (68°F to 77°F) and is to be protected from light.⁴⁶ The product will be stored by BJH Investigational Drug Service in a secure location under proper & monitored environmental conditions.

Each multi-dose vial has a beyond-use date of 28 days after initial use.

6.2.4 PREPARATION

Medication preparation will be performed by the BJH Investigational Drug Service using proper aseptic technique in accordance with USP Chapter 797. Ketamine will be diluted using normal saline to a concentration of 5 mg/mL (e.g., 500 mg in 100 mL). Both ketamine and normal saline placebo will be delivered in 100 mL bags that have identical appearance except for a unique study identifier.

6.3 MEASURES TO MINIMIZE BIAS: RANDOMIZATION AND BLINDING

Randomization will occur postoperatively at the time of study medication preparation. Patients will be randomized in a 1:1 ratio to ketamine or normal saline placebo. Randomization will occur in blocks of 4. The randomization scheme will be held by the Investigational Drug Service.

Patients, research team members, and clinical staff (nurses, physicians) will be blinded to treatment allocation. To facilitate blinding, study medication for both the ketamine group and the control group will be delivered in 100 mL bags with identical appearance except for a unique study identifier.

Intentional unblinding of the clinical staff may occur in the case of serious adverse events if the attending physician feels knowledge of the treatment allocation will impact clinical decision making. The principal investigator will be notified of all instances of intentional unblinding.

Inadvertent unblinding may occur if the patient experiences side effects such as nystagmus, hallucinations, sedation, or hypertension/tachycardia. To detect inadvertent unblinding of the patient, we will ask the patient during the final study visit if they believe they received ketamine or placebo. To minimize the effects of inadvertent unblinding on study results, endpoints will be measured by study staff who were not present during the study medication infusion.

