9.2 SAMPLE SIZE DETERMINATION

The sample size of 32 has been selected to allow the primary descriptive endpoints to be measured with acceptable levels of precision:

- Primary Endpoint 1: Fraction of approached patients who enroll in the trial

- Conservatively assuming that 25% of approached patients will enroll, then $n = 32$ patients will allow this proportion to be measured with a 95% confidence interval width of $\pm 15\%$:

$$95\%CI = \pm 1.96 \sqrt{\frac{p(1-p)}{n}} = \pm 1.96 \sqrt{\frac{(0.25)(0.75)}{32}} = \pm 0.15$$

- Primary Endpoint 2: Fraction of planned study medication infusions that are completed
 - If we assume that 90% of planned infusions are completed, then $n = 32$ patients will allow this proportion to be measured with a 95% confidence interval width of $\pm 10\%$:

$$95\%CI = \pm 1.96 \sqrt{\frac{p(1-p)}{n}} = \pm 1.96 \sqrt{\frac{(0.90)(0.10)}{32}} = \pm 0.10$$

- Primary Endpoint 3: Fraction of participants with MADRS scores available at all specified time points
 - If we assume that 95% of participants will have scores available at all specified time points, then $n = 32$ patients will allow this proportion to be measured with a 95% confidence interval width of $\pm 7\%$:

$$95\%CI = \pm 1.96 \sqrt{\frac{p(1-p)}{n}} = \pm 1.96 \sqrt{\frac{(0.95)(0.05)}{32}} = \pm 0.07$$

This sample size does not provide power to test the secondary endpoints for superiority. However, the observed values will be used to determine effect sizes, as well as standard deviations for the observed values. These quantities will inform the sample size calculation for the full-scale clinical trial. A minimum of 24-30 patients has previously been recommended for estimating effects sizes,^{61,62} so this feasibility trial should be large enough to provide the necessary estimates.

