9.4 STATISTICAL ANALYSES

9.4.1 GENERAL APPROACH

For descriptive statistics, categorical data will be presented using frequency counts and percentages, normally distributed continuous data will be presented using means and standard deviations, and non-normally distributed continuous data will be presented using medians and interquartile ranges.

Normality will be assessed using visual analysis of histograms and using the Kolmogorov-Smirnov test. All inferential tests will be two-tailed, and p-values < 0.05 will be considered statistically significant.

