9.4.3 ANALYSIS OF THE SECONDARY ENDPOINT(S)

Secondary Endpoint 1:

For each randomized participant, the difference in MADRS score on post-infusion day 4 and at the preoperative baseline visit will be calculated. Participants with missing MADRS scores at either time point will be excluded. (No imputation of MADRS scores will be performed.)

The distribution of delta MADRS scores in the population will be assessed for normality using visual analysis of histograms and using the Kolmogorov-Smirnov test. If the delta MADRS scores are normally distributed, then the mean delta scores in the two groups will be compared using a two-sample t-test. If the delta MADRS scores are not normally distributed, then the median delta scores in the two groups will be compared using a Wilcoxon rank sum test.

Secondary Endpoint 2:

For each randomized participant, the EEG collected on the second night following the study medication infusion will be analyzed by an experienced sleep technician to identify sleep stages. Within each time

epoch captured, slow wave activity will be defined as the total power in the 1-4 Hz frequency band. The delta sleep ratio (DSR) will be defined as the ratio of SWA during the first non-rapid eye movement (NREM) epoch to SWA during the second NREM epoch.

The distribution of DSRs in the population will be assessed for normality using visual analysis of histograms and using the Kolmogorov-Smirnov test. If the DSRs are normally distributed, then the mean DSR in the two groups will be compared using a two-sample t-test. If the DSRs are not normally distributed, then the median DSR in the two groups will be compared using a Wilcoxon rank sum test.

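### Infusion can fall on postoperative day 0 to 3, but neither randomisation nor the secondary analyses take account of it: a minor, cheap improvement

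*Combined protocol and SAP*

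**What the plan says.** Below, *path* means where the patient is extubated: in the operating room (OR path) or after transfer to the ICU while intubated (ICU path).

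- **Timing of study drug (6.1.2).** For the OR path, "For patients who are extubated in the operating room, the study medication will be initiated prior to leaving the operating room". The ICU path uses early-morning slots on postoperative day 1, 2 or 3. For the last of these, "the study medication will be administered between 05:00am and 08:00am on postoperative day 3". A patient who is too sedated beforehand is re-evaluated the next day, with postoperative day 3 as the limit.
- **Allocation (6.3).** "Patients will be randomized in a 1:1 ratio to ketamine or normal saline placebo. Randomization will occur in blocks of 4". No stratification factor is named. On timing, "Randomization will occur postoperatively at the time of study medication preparation"; 4.1 also places randomisation after extubation.
- **Secondary endpoints (9.1, 9.4.3).** MADRS change runs from the preoperative assessment to post-infusion day 4. The delta sleep ratio is taken from the second night after the infusion. For MADRS, "If the delta MADRS scores are normally distributed, then the mean delta scores in the two groups will be compared using a two-sample t-test"; otherwise a Wilcoxon rank sum test is used. The sleep ratio is handled the same way. Neither analysis has a covariate.
- **Subgroups (9.4.7).** By surgical service only, and for the feasibility endpoints only.
- **Use of the results (9.2).** The secondary endpoints are declared unpowered, but their effect sizes and SDs will feed the sample size of the full-scale trial.

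**The concern.** The MADRS change starts from a preoperative baseline and ends on a day counted from the infusion. The span from surgery to assessment therefore varies by up to three days between patients. It varies together with recovery, because the later patients are those who needed ventilation after surgery. Path and day of infusion are fixed before any drug is given, so they could be balanced by design or adjusted for, and the plan does neither.

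With about 16 patients per arm, chance can put clearly more ICU-path patients in one arm. Part of the observed difference would then reflect time since surgery and ICU recovery. Even when the arms are balanced, variation between paths stays in the error term. Both effects would carry into the estimates used to plan the full-scale trial.

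**Working it through.** **Inputs from the documents.** Total 32 (9.2: "The sample size of 32 has been selected to allow the primary descriptive endpoints to be measured with acceptable levels of precision"), 1:1 in blocks of 4, infusion on postoperative day 0 to 3, two-sided 0.05 (9.4.1).

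**Inputs assumed.** The documents give neither the share of patients on the ICU path nor any effect of path on the outcomes. I take 4, 8 or 16 of 32 on the ICU path, and a path effect D of 0.25, 0.5 or 1.0 within-path SD.

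**1. The plan's own figure.** No figure is given for timing or balance. The nearest is the precision of Primary Endpoint 1 (9.2: "Conservatively assuming that 25% of approached patients will enroll"): 1.96 × √(0.25 × 0.75 / 32) = 0.150. The stated ±15% is reproduced.

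**2. Calendar.** Postoperative day of the day-4 MADRS = day of infusion + 4.

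| Infusion, postoperative day | Day-4 MADRS, postoperative day | Second post-infusion night (night after surgery = 1) |
|---|---|---|
| 0 | 4 | 2 |
| 1 | 5 | 3 |
| 2 | 6 | 4 |
| 3 | 7 | 5 |

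The EEG column follows 9.1 and 9.4.3. The synopsis instead gives postoperative day 1, and the Section 3 table gives post-infusion night 1. These must be reconciled, but under any night counted from the infusion the shift between patients is the same.

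**3. Chance imbalance.** With K ICU-path patients, the number X in one arm is hypergeometric (32, K, 16). A simulation of 100,000 block-of-4 lists gave the same results for K = 8 and 16.

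| K | P(arms differ by ≥ 4) | P(arms differ by ≥ 6) |
|---|---|---|
| 4 | 0.10 | 0 |
| 8 | 0.22 | 0.04 |
| 16 | 0.29 | 0.08 |

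For K = 4 this is 2 × C(16,4)/C(32,4) = 3640/35960 = 0.101. With separate lists in blocks of 4, the arms can differ by at most 2 within a path, so a gap of 4 cannot occur.

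**4. Shift in the estimate.** A 10–6 split gives (10/16 − 6/16) × D = 0.25D, which is 0.06, 0.125 or 0.25 SD. For comparison, the 95% half-width of the standardised difference is 1.96 × √(2/16) = 0.69 SD.

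**5. SD inflation from ignoring path.** The factor is √(1 + q(1−q)D²), where q is the ICU share. For q from 0.25 to 0.5 it is about 1% (D = 0.25), 2–3% (D = 0.5) or 9–12% (D = 1.0).

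**6. SE after adjustment, relative to the unadjusted SE.**
- *Stratified lists plus adjustment:* 1/√(1 + q(1−q)D²). This is 1.00 at D = 0. For q from 0.25 to 0.5 it is about 0.99 at D = 0.25, 0.97–0.98 at D = 0.5 and 0.89–0.92 at D = 1.0.
- *Adjustment alone, averaged over unstratified lists (simulated, same shares):* about +2% at D = 0, +1% at 0.25, −1% to −2% at 0.5 and −6% to −9% at 1.0.
- *Adjustment alone, given a 10–6 split:* arm and path correlate at 0.25, so variance is multiplied by 1/(1 − 0.0625). The SE ratio is √(1/0.9375) / √(1 + 0.625 × 0.375 × D²) = 1.025, 1.004 or 0.93 for D = 0.25, 0.5 or 1.0.

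**The case against.** A reader might infer that staggered timing biases the treatment comparison or invalidates the unadjusted test. The documents do not support that. The timing rule is identical in both arms, allocation is random and follows surgery, and the ordinary SE already covers chance imbalance. Anchoring outcomes to the infusion also suits a hypothesis about drug effect, and leaving 32 patients unstratified is a defensible choice.

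Other points that stand:

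- None of the three feasibility endpoints is affected, and the secondary endpoints are openly unpowered.
- The central shift of 0.125 SD is about a third of the SE (0.35 SD). SD inflation of 2–3% is small beside the 95% uncertainty of an SD on 30 degrees of freedom, roughly −20% to +34%.
- If the full-scale trial keeps this timing rule and an unadjusted analysis, the total SD is the right planning input. An adjusted SD alone would understate it.
- Adjustment without stratification does not reliably reduce the SE (step 6).
- Two lists do not balance day 1 against 2 against 3, and sedation can also delay an OR-path patient. Days from surgery to infusion is therefore the fuller covariate.
- 9.4.2 refers to participants under protocol versions 1 and 2, so some may already be randomised. If OR-path bags are prepared before extubation, separate lists are also harder to run.

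What does not follow is that nothing is worth changing. Stratified lists with adjustment remove the chance imbalance with essentially no loss of precision at any path effect considered.

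**Conclusion.** A cheap improvement of minor weight. The facts are clear in the text: infusion on postoperative day 0 to 3, day-4 MADRS on postoperative day 4 to 7, no stratification factor, and no adjustment in either secondary analysis. The consequence is chance imbalance and modest extra variance, not bias or loss of type I error control.

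The probability of a gap of 4 or more ICU-path patients (0.10 to 0.29) depends on an assumed path share. The resulting shift (0.06 to 0.25 SD) depends on an assumed path effect, and it is well inside the sampling error of ±0.69 SD. The point deserves action only because these estimates will help size the full-scale trial and the remedy costs little.

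**What to change.** 1. **6.3.** For patients not yet randomised, have the Investigational Drug Service hold two lists in blocks of 4: one for extubation in the operating room, one for ICU transfer while intubated.
2. **9.4.3.** Estimate both secondary treatment differences with a linear model that includes days from surgery to infusion (or path). Name one of the two in advance. If the data are not normal, use a rank test stratified by path in place of the plain Wilcoxon test.
3. **If the lists can no longer change.** Prespecify the adjusted model as a sensitivity analysis for chance imbalance, and claim no SE gain.
4. **9.2.** State that both the total and the adjusted SD will be reported, since a full-scale trial analysed without adjustment needs the total SD.
5. **EEG night.** Reconcile the synopsis, the Section 3 table, 9.1 and 9.4.3.

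**Cost.** A second pharmacy list and one degree of freedom. Two incomplete final blocks could leave the arms at worst 18:14, with relative efficiency 18 × 14 / 16² = 0.984, a loss under 2%. Covariate-only adjustment can enlarge the SE by about 1% to 2% if path has little effect. The timing of drug administration stays as written.

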5.5 STRATEGIES FOR RECRUITMENT AND RETENTION

Anticipated Patient Population – The target sample size will be 32 patients. Patients will be enrolled at a single site (BJH/Washington University School of Medicine). The expected accrual rate was estimated by examining characteristics (obtained via Epic Slicer Dicer at the population level only) of a retrospective cohort of patients who had non-emergent surgery at BJH between 1/1/2021 and 6/30/2021, had an ICU admission, and had an ICD grouper corresponding to depression documented in the diagnosis list or the past medical history. The query was limited to the cardiac, neurosurgery, and vascular services because many of the patients from other services (e.g., trauma, orthopedic) were suspected to have initially had emergent surgery followed by an ICU admission and then a non-emergent surgery. Exclusion criteria for the retrospective query included age < 18. During that 6-month time period, there were 307 patients who met these criteria (Figure 2). If we conservatively estimate that 20% of these patients enroll in the trial, that results in an accrual of 10 patients per month.

The gender, race and ethnicity, and age distributions are expected to follow the gender, race and ethnicity, and age distributions served by the Barnes-Jewish Hospital. These distributions were observed in the retrospective cohort seen in Figure 2. The anticipated characteristics of the study population are shown in Table 1.

[figure not shown]

Figure 2. Number of potentially eligible patients in a 6-month period.

Table 1. Anticipated Demographic Characteristics of the Study Population

Racial Categories	Ethnic Categories				Total	
	Not Hispanic or Latino		Hispanic or Latino			
	Female	Male	Female	Male		

American Indian/ Alaska Native	1	0	0	0	1
Asian	1	0	0	0	1
Native Hawaiian or Other Pacific Islander	0	0	0	0	0
Black or African American	2	2	0	0	4
White	13	11	1	1	26
More than One Race	0	0	0	0	0
Total	17	13	1	1	32

Recruitment Strategy – Patients will primarily be recruited at the Center for Preoperative Assessment and Planning (CPAP). Potentially eligible patients will be identified by screening the CPAP schedule. Patients identified via screening will be approached by telephone prior to their CPAP appointment or in person at CPAP.

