7.2 PARTICIPANT DISCONTINUATION/WITHDRAWAL FROM THE STUDY

Participants are free to withdraw from participation in the study at any time upon request.

An investigator may discontinue or withdraw a participant from the study for the following reasons:

- If any clinical adverse event (AE), laboratory abnormality, or other medical condition or situation occurs such that continued participation in the study would not be in the best interest of the participant
- If the participant meets an exclusion criterion (either newly developed or not previously recognized) that precludes further study participation

The reason for participant discontinuation or withdrawal from the study will be recorded on the Case Report Form (CRF). Subjects who sign the informed consent form and are randomized but do not receive the study intervention may be replaced. Subjects who sign the informed consent form, and are randomized and receive the study intervention, and subsequently withdraw, or are withdrawn or discontinued from the study, will not be replaced.

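### The fixed, disclosed block length of 4 with a recognisable active arm lets staff who see infusions sometimes deduce later allocations; varying, undisclosed block sizes would be a cheap improvement

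*Combined protocol and SAP*

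**What the plan says.** Section 6.3 sets the ratio ("Patients will be randomized in a 1:1 ratio to ketamine or normal saline placebo") and a single block length ("Randomization will occur in blocks of 4"). It mentions no varying of the length and no stratification. Section 4.1 describes one site, and section 5.5 sets the size: "The target sample size will be 32 patients".

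The same section describes concealment: "The randomization scheme will be held by the Investigational Drug Service", and "Randomization will occur postoperatively at the time of study medication preparation". Section 6.2.1 has the drug prepared "after an order has been placed in Epic by the research team".

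On masking, section 6.3 concedes that "Inadvertent unblinding may occur if the patient experiences side effects such as nystagmus, hallucinations, sedation, or hypertension/tachycardia". Section 4.2 makes a similar concession about the saline control, and section 7.1 adds that halting the drug may unblind patient and clinical staff. As safeguards, section 6.3 specifies bags of identical appearance and has endpoints measured by study staff who were not at the infusion. The only unblinding check is the patient's own guess at the final visit.

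Under section 8.2 a research team member scores the BPRS subscale and CADSS-6 and runs the side-effect checklist midway through the infusion. Section 7.2 states: "Subjects who sign the informed consent form and are randomized but do not receive the study intervention may be replaced".

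**The concern.** With two ketamine and two saline places in every block of 4, anyone who knows the length and recognises two patients on the same arm knows the rest of that block. Holding the list in the pharmacy does not prevent this, because the deduction needs only the published length and the order of patients. One site and no described strata make that order easy to follow.

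A patient's own side effects unblind only that patient. A fixed block spreads the knowledge to patients whose infusions were uneventful or have not yet happened. The places where it could matter are:

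- **Scoring at the infusion.** BPRS, CADSS-6 and the checklist are compared between arms (section 9.4.4), and their assessors see side effects directly.
- **MADRS and CGI ratings, indirectly.** The rule in section 6.3 can be read patient by patient. Nothing in the documents bars someone who attended one patient's infusion from rating another patient in the same block, or bars raters from the health record or colleagues' observations.
- **Ordering and replacement, at the margin.** The research team places the order that precedes randomization, and randomized but undosed patients may be replaced.

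Section 9.2 uses the observed effect sizes and standard deviations to plan the full-scale trial, so a biased MADRS contrast could carry forward. Staff deductions would go unnoticed, since only patients are asked to guess.

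**Working it through.** The documents give no predictability figure, so there is none to reproduce.

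**Inputs.** Block length 4 and ratio 1:1 (section 6.3); 32 patients (section 5.5), so 32/4 = 8 blocks. The recognition probability q for this dose is not stated and is an assumption below. The only percentage given is about 12% for psychotomimetic effects at anesthetic doses (section 2.3.1). It is neither an estimate for this dose nor a ceiling, because that section separately calls nystagmus and diplopia common.

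**Step 1: enumerate the six equally likely blocks** (K ketamine, S saline). Count the positions that are certain because one arm is used up.

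| Block | Certain, all earlier allocations known | Certain, from two recognised ketamine patients only |
|---|---|---|
| KKSS | 2 | 2 |
| KSKS | 1 | 1 |
| KSSK | 1 | 0 |
| SKKS | 1 | 1 |
| SKSK | 1 | 0 |
| SSKK | 2 | 0 |
| Total of 24 positions | 8 | 4 |

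- All earlier allocations known: 8/24 = 33.3%, or 10.7 of 32. This is an expected value; single blocks range from 1/4 to 2/4.
- Only ketamine recognisable, and always recognised: 4/24 = 16.7%, or 5.3 of 32. Going beyond this requires treating absence of side effects as proof of saline.

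**Step 2: imperfect recognition.** A deduction needs both patients on the exhausted arm to be recognised, which gives a factor q².

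- Ketamine only, (4/24)q²: q = 0.5 gives 4.2% (1.3 of 32); q = 0.7 gives 8.2% (2.6 of 32); q = 0.12 gives 0.2% (0.08 of 32).
- Both arms equally recognisable, (8/24)q²: q = 0.5 gives 8.3% (2.7 of 32); q = 0.12 gives 0.5%.

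**Step 3: best guessing with all earlier allocations known.** The chances of a correct guess at positions 1 to 4 are 1/2, 2/3, 2/3 and 1. At position 3, the first two match with probability 1/3 and the guess is then certain; otherwise it is a coin toss, so 1/3 + (2/3)(1/2) = 2/3. The mean is 2.833/4 = 70.8%, against 50% by chance.

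**Step 4: varying block sizes.** Trials of 32 were simulated with an observer who knows every earlier allocation and the set of possible sizes, but not the block boundaries.

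| Block sizes | Certain | Best guess correct |
|---|---|---|
| Fixed 4 | 33% | 71% |
| 2, 4, 6 | about 4% | 70% |
| 4, 6, 8 | about 2% | 67.5% |

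The gain is the near-removal of certainty. The guessing advantage shrinks little.

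**The case against.** The strongest reply is that the plan already breaks the main chain. Staff who watch infusions do not measure that patient's endpoints, so a MADRS rater would have to learn of earlier reactions second-hand, or from other patients' infusions, and also follow the allocation order. The documents do not close that route, but they do not show that it is used. This part of the reply stands.

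Three stronger readings are tempting and are not supported.

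- **That MADRS raters can deduce a third of allocations.** A third is the expectation when every earlier allocation is known, saline included. Nothing in the documents suggests such recognition. Section 2.3.1 reports no clinically significant blood pressure or heart rate changes at doses this low, and section 8.2 does not expect clinically significant sedation.
- **That staff can steer who enters the trial.** Randomization follows consent and surgery. Section 6.1.2 ties drug timing to extubation and deferral to the sedation score. Replacement adds a patient, while section 9.3 still analyses everyone randomized. Only marginal discretion over ordering or replacement is left.
- **That one intentional unblinding reveals the rest of the block.** It makes no other allocation certain: of the other three places, two are the other arm and one the same, which is odds of 2:1. Section 6.3 provides such unblinding for clinical staff, and nothing says that the arm is passed to raters.

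It is also fair to say that the fix leaves a patient's own side effects as revealing as before. The primary endpoints are pooled feasibility proportions, and section 9.1 states that the efficacy comparisons are unpowered.

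**Conclusion.** The point holds as a modest weakness. A fixed block length of 4, printed in the protocol and used at one site with a recognisable active arm, lets knowledge of some patients carry over to others in the block. The size depends on a recognition rate that the documents do not give: an expected 33% certain at the extreme of full knowledge, at most 17% if only ketamine is recognisable, about 4% to 8% (1 to 3 patients of 32) at q from 0.5 to 0.7, and 0.2% at q = 0.12. All of these assume that the observer knows the block length and follows the order of allocation.

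The feasibility conclusions are little affected. The quantities exposed are the safety scales scored at the infusion and, indirectly, the secondary MADRS effect estimate. This is a worthwhile, optional improvement, and not a flaw that invalidates the trial or shows that ratings will be biased.

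**What to change.** In section 6.3, replace the block sentence with: allocation uses randomly permuted blocks of varying size, with the sizes known only to the Investigational Drug Service and the person who generates the list. Remove the block length from the protocol given to the research team. If enrolment has begun, as the reference to participants under protocol version 1 in section 9.4.2 suggests, apply the change from the next unused block; completed blocks gain nothing.

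The cost is an amendment with IRB approval (Statement of Compliance) and a new pharmacy list. The arms may also differ at the end by up to half the largest block: 8/2 = 4 patients if the largest block is 8, or 6/2 = 3 if it is 6. The change does not address unblinding from a patient's own side effects.
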